4.2 Inclusion Criteria

Each patient must meet the following criteria to be enrolled in this study:

- 1. Written informed consent
- 2. Diagnosed with RA for ≥ 6 months according to ACR/European League Against Rheumatism (EULAR) Classification Criteria 2010 (Appendix 4)
- 3. 18 to 75 years of age, inclusive, at the time of informed consent
- 4. Swollen joint count of ≥ 6 (66-joint count) and tender joint count of ≥ 6 (68-joint count) at Screening and randomization
- 5. This criterion was removed in Amendment #3
- 6. Inadequate response to therapy or discontinuation of therapy because of unacceptable toxicity from at least one prior traditional or biologic DMARD
- 7. Remain on a stable dose of methotrexate (≥ 15 mg/week and ≤ 25 mg/week) for ≥ 6 weeks before randomization; a lower dosage of methotrexate (≥ 10 mg/week) is allowed if there is documented intolerance to dosages of ≥ 15 mg/week; folic acid ≥ 5 mg/week (or an equivalent dose of folinic acid) is required for all patients. If taking hydroxychloroquine in combination with methotrexate, the patient must remain on a dose of ≤ 400 mg/day hydroxychloroquine that has been stable for ≥ 6 weeks before randomization. (Note: If discontinued from hydroxychloroquine, the patient must remain on this revised treatment regimen for at least 4 weeks before randomization.)

All other DMARDs must have been discontinued for at least the following periods of time:

- Oral DMARDs and etanercept at least 4 weeks before randomization
- Rituximab and any other lymphocyte/B-cell-depleting therapy at least 1 year before randomization
- All other biologic DMARDs, including infliximab, adalimumab, golimumab, certolizumab pegol, abatacept, and tocilizumab, at least 8 weeks before randomization
- Patients who have been on leflunomide must have not received leflunomide for at least 4 weeks before randomization and must undergo treatment to facilitate drug elimination with 8 g cholestyramine three times daily for 3 days to be eligible for participation.

8. Male or Female

Females of childbearing (reproductive) potential must have a negative serum pregnancy test at screening and agree to use an acceptable method of contraception throughout their participation in the study. Acceptable methods of contraception include double barrier methods (condom with spermicidal jelly or a diaphragm with spermicide), hormonal methods (eg, oral contraceptives, patches or medroxyprogesterone acetate), or an intrauterine device (IUD) with a documented failure rate of less than 1% per year. Abstinence or partner(s) with a vasectomy may be considered an acceptable method of contraception at the discretion of the investigator. Men of reproductive potential must also agree to use an acceptable method of contraception.

Amendment 5: 28 Mar 2016

Note: Females who have been surgically sterilized (eg, hysterectomy or bilateral tubal ligation) or who are postmenopausal (total cessation of menses for > 1 year) will not be considered "females of childbearing potential".

4.3 Exclusion Criteria

Patients who meet any of the following criteria will be excluded from the study.

Medical History

- 1. Functional Class IV as defined by ACR classification of functional status in RA (Appendix 5)
- 2. History of significant systemic involvement secondary to RA (e.g., vasculitis, pulmonary fibrosis, or Felty's syndrome)
- 3. History of malignancy or carcinoma in situ within the 5 years before Screening or a history of melanoma. Patients with history of excised or adequately treated non-melanoma skin cancer are eligible
- 4. Evidence of clinically significant uncontrolled concurrent diseases such as cardiovascular, endocrinologic, hematologic, hepatic, immunologic, metabolic, urologic, pulmonary, neurologic, dermatologic, psychiatric, renal, and/or other major diseases
- 5. History of recurrent clinically significant infections
- 6. Current active infection or serious local infection (e.g., cellulitis, abscess) or systemic infection (e.g., pneumonia, septicemia) within 3 months before randomization
- 7. Fever (body temperature > 38°C) or symptomatic viral or bacterial infection within 14 days before randomization
- 8. History of drug or alcohol abuse (as defined by the Investigator) within the 1 year before Screening
- 9. History of severe allergic or anaphylactic reactions to other biologic agents
- 10. History of allergies to murine protein
- 11. Surgery within 3 months before randomization (other than minor cosmetic surgery or minor dental procedures) or plans for a surgical procedure during the Treatment Period or Follow-up Period
- 12. History of malaria; patients with a history of travel to a malaria-endemic region within 4 months before randomization may be considered for enrollment upon consultation with the Sponsor regarding confirmation of no active disease via a polymerase chain reaction (PCR). Patients should not plan to travel to a malaria-endemic region throughout the duration of the study, including Screening and the 4-week Follow-up Period.
- 13. History of tuberculosis or latent infection currently undergoing treatment

Treatment History

- 14. This criterion was removed in Amendment #3.
- 15. Treatment with another investigational agent, investigational device, or approved therapy for investigational use within the 4 weeks before randomization or within 5 half-lives of the investigational agent (longer of the two).
- 16. Treatment regimen with prednisone that is either over 10 mg/day (or equivalent dose of another corticosteroid) or is not taken at a stable dose of ≤ 10 mg/day for at least 4 weeks before randomization.
- 17. Intra-articular corticosteroid injection(s) within 4 weeks before randomization
- 18. Current use of opioids or other narcotics. Note: Patients receiving NSAIDS or the following opioids (tramadol, codeine and oral acetaminophen/codeine combination) at stable doses for at least 2 weeks prior to randomization will be eligible for inclusion.

Amendment 5: 28 Mar 2016

19. Any live immunization/vaccination, including against Herpes zoster, within 4 weeks before randomization. Live vaccinations must also be avoided throughout the study.

Laboratory Values

- 20. Abnormal laboratory value at Screening or Day -1 considered clinically significant (as determined by the Investigator), or:
 - Serum creatinine > 1.6 mg/dL
 - Aspartate aminotransferase (AST) or alanine aminotransferase (ALT) > 1.5 × ULN
 - Platelet count < 100,000/μL
 - Hemoglobin < 8.5 g/dL
 - ANC $< 2.0 \times 10^3/\mu L$
- 21. Women of childbearing potential who test positive for a serum pregnancy test at Screening or a urine pregnancy test within 12 hours before randomization.
- 22. Positive for hepatitis C virus (HCV) antibody or hepatitis B surface antigen (HBsAg) (Note: patients with positive HCV antibody may be considered for enrollment upon consultation with the Sponsor regarding confirmation of no active disease via a PCR test).
- 23. Positive for human immunodeficiency virus (HIV) antibody.
- 24. Positive QuantiFERON®-TB Gold test (QFT) (Note: If the QFT result is indeterminate and the chest X-ray is without clinically significant findings, a second QFT may be performed. If the second QFT result is negative, the patient may be considered for enrollment. If the second QFT is positive or indeterminate, the patient is ineligible.)
- 25. Current enrollment in any other study wⁱth an investigational agent, investigational device, or approved therapy for investigational use
- 26. Previous exposure to SAN-300
- 27. Unwillingness or inability to comply with the requirements of this Protocol, including the presence of any condition (physical, mental, or social) that is likely to affect the patient's returning for follow-up visits on schedule
 - NOTE: Patients who cannot tolerate the magnetic resonance imaging (MRI) procedures due to physical or other limitations may be enrolled in the study.
- 28. Other unspecified reasons that, in the opinion of the Investigator or the Sponsor, make the patient unsuitable for enrollment
- 29. Blood donation (450 mL or more) within 1 month before Screening
- 30. Nursing mothers or women who are planning to become pregnant during the study

5 TREATMENTS TO BE ADMINISTERED

5.1 Planned Dose Cohorts

Eligible patients will be enrolled into a dose cohort and randomized (3:1) to receive either SAN-300 via SC injection over 6 weeks or a matching volume of placebo. More than one SC injection may be required (maximum volume of 1.2 mL per SC injection) depending on the total dose administered and the weight of the individual patient. Dosing by cohort is provided in Table 2.

Table 2. Dose Cohorts for Study C2013-0302

	Number of Patients to be Dosed		
Cohort	SAN-300	Placebo	SAN-300 Dose
А	6	2	0.5 mg/kg SC once weekly
В	6	2	1.0 mg/kg SC once weekly
С	6	2	2.0 mg/kg SC every other week
D	6	2	4.0 mg/kg SC every other week
Е	6	2	4.0 mg/kg SC once weekly
F	6	2	2.0 mg/kg SC once weekly

Abbreviations: SC = subcutaneous

Safety and tolerability findings will be reviewed in a blinded manner for all patients in a cohort after the 6-week Treatment Period to determine whether or not enrollment will begin in the next cohort. Any subject who withdraws prior to the end of the 6-week Treatment Period will not be replaced and the Study Safety Committee will review the data from all subjects regardless of duration of participation in the study. The safety review will include, at minimum, the following information: AEs; safety laboratory results; vital sign measurements; and reasons for premature study withdrawal.

The decision to begin enrollment in the next cohort will be based upon the results of the safety review. In addition, based on the findings of the Study Safety Committee, the Sponsor may elect to modify the dose in the next cohort to a lower dose or terminate any further dose escalation.

Refer to Section 3.4 for patient and study stopping rules.

5.2 Method of Assigning Patients to Treatment Groups

Fixed allocation will be used to randomize patients in a ratio of three on SAN-300 to one on placebo within each cohort of approximately 8 total patients.

Cohort A will be enrolled first, with 6 patients randomly assigned to receive SAN-300 and 2 patients randomly assigned to receive matching placebo in two blocks of four patients (three on SAN-300, one on placebo). After Cohort A has completed the 6-week Treatment Period, a Study Safety Committee will conduct a blinded safety review. If the Study Safety Committee determines that the safety profile is acceptable, then Cohort B can begin enrollment. Additional Safety Committee reviews will occur following completion of the 6-week Treatment Period for each of the subsequently enrolled cohorts.

Santarus, Inc.
SAN-300
CONFIDENTIAL
SINCE CONFIDENTIAL
Clinical Trial Protocol: C2013-0302

SAN-300 Amendment 5: 28 Mar 2016

Randomization will be central and occur after a patient has been deemed eligible. Randomization will be performed by Interactive Voice/Web Response System (IVRS/IWRS). The unblinded pharmacist or designated study center personnel assigned to this role will be responsible for obtaining the treatment assigned to each patient in each cohort by contacting the IVRS/IWRS system by phone or Web site. This unblinded person will then prepare the study drug and provide it to the Investigator. The study drug will then be administered by qualified, blinded study personnel on the day of or within 24 hours after randomization.

5.3 Blinding

Study drug will be prepared by unblinded pharmacy staff or designated study center personnel.

The randomization code that assigns treatments to patients will be available in confidence only to personnel responsible for preparation of the study drug for administration. Except in circumstances of immediate threat to patient safety (e.g., medical emergencies) detailed in Section 5.4, the code will not be broken until after all data entry is completed, the validity of the data is checked, all queries are resolved, the statistical analyses are defined, and the database is locked.

5.4 Breaking the Blind

Only in the case of an emergency, when knowledge of the study drug is essential for the clinical management or welfare of the subject, will the investigator be allowed to unblind a subject's treatment assignment. To discuss breaking of the blind please contact the Clinical Project Manager at Santarus, Inc. by using the following contact information:

Protocol C2013-0302 Medical Monitor [name] Santarus, Inc., a wholly owned subsidiary of Valeant Pharmaceuticals International [name] Phone: + 1 [contact]

If the investigator breaks the blind for an individual subject, the reason must be recorded in the subject's source documents and the subject will be removed from the study.

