3.4.1 Stopping Rules for Individual Patient Dosing

The dosing of an individual patient will be stopped under the following circumstances:

- The patient experiences a confirmed reduction in ANC to < 1.0 × 10³/μL.
- The patient experiences a clinically significant atypical or opportunistic infection (including those listed in Appendix 1).
- The patient experiences a clinically significant adverse event related to study participation, in the opinion of the investigator or Sponsor.

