3.5 Study Safety Committee

The Study Safety Committee will be composed of, at a minimum, a Sponsor representative and two independent expert physicians. This committee will review ongoing blinded study safety data, decide whether dose escalation is appropriate (see Section 3.1 for the role of safety reviews in dose escalation), recommend any modifications in dosing, and evaluate whether resumption of individual patient dosing or study enrollment is permissible after any interruption triggered by the stopping rules for patient dosing and for study enrollment (see Section 3.4).

Santarus, Inc.
SAN-300 Clinical Trial Protocol: C2013-0302

Amendment 5: 28 Mar 2016

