7 PATIENT WITHDRAWAL AND STUDY TERMINATION

7.1 Reasons for Withdrawal

Participation in the study is strictly voluntary. A patient has the right to withdraw from the study at any time for any reason. If he/she chooses to withdraw, the patient must inform the Investigator immediately and will be asked to make an Early Withdrawal Visit. If feasible, it is also highly recommended that the patient schedule a Follow-up Visit for a safety evaluation 4 weeks after their last dose of study drug. The Investigator has the right to terminate participation of any patient at any time if it is deemed to be in the patient's best interest. The reason and circumstances for premature discontinuation will be documented in the patient's electronic case report form (eCRF). Possible examples for reasons of premature study withdrawal include:

- Withdrawal of consent
- Intolerable AE
- Intake of non-permitted concomitant medication
- Significant non-compliance with the protocol
- Positive pregnancy test in a female patient
- Clinical or administrative reason consistent with the requirements of the protocol at the Investigator's discretion
- Clinically significant worsening of RA that, in the opinion of the Investigator, requires immediate, specific medical treatment

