7.2 Procedures for Early Withdrawal

When it is determined that a patient should withdraw from the study, the reason(s) must be recorded, final assessments must be scheduled, and provisions for the continued treatment of RA within the standards of care must be discussed with the patient. Safety and study endpoint evaluations for the Early Withdrawal Visit (see Sections 10.2.6 and 10.3.1) will be performed as soon as possible after the decision is made to withdraw the patient.

Additional interventions (concomitant medications or therapies) may be prescribed as needed by the patient. The patient's history and preferences should be considered and discussed when prescribing a new medication for RA.

Appropriate medical follow-up with the patient should be conducted as clinically indicated after the Early Withdrawal Visit. Telephone contacts between the patient and the study staff should be conducted as frequently as needed.

If the patient is found to have an AE or clinically significant laboratory abnormality, the patient will be followed until the event/abnormality is resolved, or until the Investigator determines that further follow-up is no longer medically indicated. The responsible IEC/IRB should be notified of any AEs and/or circumstances leading to early withdrawal.

Amendment 5: 28 Mar 2016

If a patient is withdrawn from study participation because of pregnancy, Product Safety and IEC/IRB should be informed by the site within 24 hours of awareness. All pregnancies occurring in female patients must be reported. The pregnancy will be reported according to the procedures provided in Section 9.8. Should the patient have a spontaneous abortion or complications during the pregnancy, then the event must be captured as an SAE. Sites are obligated to follow the patient until the outcome of the pregnancy is known. The patient and/or her treating physician should be encouraged to report any future medical problems the child develops of which they become aware that are considered related to the study drug.

Patients who are randomized and who subsequently withdraw from the study will not be replaced.

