9.3 Method, Frequency, and Time Period for Detecting AEs and SAEs

At each visit, after the patient has had an opportunity to spontaneously mention any problems, the investigator should inquire about AEs by asking the following standard questions:

- 1. "Have you had any (other) medical problems since your last visit/assessment?"
- 2. "Have you taken any new medicines, other than those given to you in this study, since your last visit/assessment?"

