9.3.1 Time Period for Detecting and Reporting of AEs and SAEs

From the time of informed consent through study completion/withdrawal, including the follow-up period.

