9 STATISTICAL AND ANALYTICAL ISSUES

9.1 Handling of dropouts or missing data

Subjects who prematurely discontinue before the end of the treatment will be contacted via follow-up phone call as frequently as needed. If the patient is found to have an AE or clinically significant laboratory abnormality, the patient will be followed until the event/abnormality is resolved, or until the Investigator determines that further follow-up is no longer medically indicated.

For subjects who discontinue prematurely, the last completed post-baseline assessment will be used as EOT.

Missing data will not be imputed in other analyses unless specified otherwise.

For subjects who terminate early from the study, if the study day of the EOT visit falls into a specific protocol defined scheduled visit window, the EOT visit will be reassigned to that specific scheduled visit for the analyses by protocol defined scheduled visit.

For cases where the start date of an AE is not complete, the assumption is made that the AE is a treatment-emergent event unless there is evidence to the contrary.

For cases where the start or the stop date of medication is not complete, the assumption is made that the medication is a concomitant medication unless there is evidence to the contrary.

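### Emergency unblinding takes the patient out of the study, not only off study drug, so scheduled safety and late antibody follow-up lapses: a cheap, low-severity improvement

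*Protocol*

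**What the plan says.** Protocol 5.4 (Breaking the Blind) limits code breaks to emergencies in which the patient's care depends on knowing the treatment. The reason then goes into the source documents "and the subject will be removed from the study". SAP 3.4 repeats the sentence.

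Elsewhere, stopping drug is a separate step. Protocol 3.4.1 says "The dosing of an individual patient will be stopped under the following circumstances", and lists a confirmed neutrophil count below 1.0 × 10³/µL, an opportunistic infection and a related significant AE. It does not mention removal. Section 3.5 asks the Study Safety Committee to "evaluate whether resumption of individual patient dosing or study enrollment is permissible after any interruption", which presupposes a patient who is still in the study.

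For a patient who does leave:

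- Section 3.1 requires the Exit Visit assessments. Sections 10.2.7 and 10.3.2 list the early withdrawal procedures for the Treatment and Follow-up Periods.
- Section 9.5 requires known AEs to be followed until they resolve, stabilise or are explained, or contact is lost.
- Section 7.1 says that, if feasible, "it is also highly recommended that the patient schedule a Follow-up Visit" 4 weeks after the last dose.
- Section 7.2 says "Telephone contacts between the patient and the study staff should be conducted as frequently as needed". SAP 9.1 says that subjects who stop before the end of treatment "will be contacted via follow-up phone call as frequently as needed".

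For patients in the study, Section 9.3 says that at each visit "the investigator should inquire about AEs by asking the following standard questions". Section 9.3.1 gives the detection period as "From the time of informed consent through study completion/withdrawal, including the follow-up period". Section 9.3.2 does not oblige sites to look for serious AEs in former participants.

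**The concern.** Safety is the primary objective and immunogenicity a secondary one. A code break is reserved for an emergency, so the patient concerned may be one whose later course is worth observing on schedule. Removal replaces that schedule with one set of assessments and contact at discretion. Knowing the treatment is a reason to stop drug and to treat later subjective scores with care. It is not in itself a reason to stop collecting blood counts, antibody samples or AE reports, and the documents give none.

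The samples at issue are relevant to this product. Section 1.3 reports transient neutrophil reductions in 12 subjects given SAN-300 in Phase 1, and treatment-emergent antibodies in two. Each cohort has 6 active patients, and Section 7.2 does not replace those who leave.

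**Working it through.** The plan states no figure on this point, so the check counts scheduled samples against what the withdrawal visit recovers, per unblinded patient.

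**Inputs**

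- Antibody, Appendix 3: Days 1, 8, 43, 64.
- Blood count (CBC), Appendix 2: Days 1, 8, 15, 22, 29, 36, 43, 57, 71.
- PK and receptor occupancy: Appendix 3.
- Withdrawal in the Treatment Period, Section 10.2.7: CBC, antibody, PK and receptor occupancy, each once.
- Withdrawal in the Follow-up Period, Section 10.3.2: CBC only of these four.
- Assumption: the withdrawal visit follows 10.2.7 and 10.3.2, which are headed for it. Section 7.2 points instead to 10.2.6 and 10.3.1, which are sampling visits.

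**Antibody.** Net loss = samples still scheduled − samples recovered at withdrawal.

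| Code break | Still scheduled | Recovered | Net loss |
|---|---|---|---|
| Days 1–7, or Day 8 before its sample | 3 (Days 8, 43, 64) | 1 | 2 |
| After the Day 8 sample to Day 42 | 2 (Days 43, 64) | 1 | 1 |
| Days 43–63, Day 43 sample taken | 1 (Day 64) | 0 | 1 |
| After the Day 64 sample | 0 | – | 0 |

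If Section 3.1 is read as Exit Visit assessments only, which include no antibody sample, the first two rows become 3 and 2. The table is therefore the lower count. The ±2-day visit window in Section 10.2 moves the edges slightly.

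**CBC, break after the Day 15 visit.** Remaining: Days 22, 29, 36, 43, 57, 71 = 6.

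- One withdrawal set: 6 − 1 = 5 lost.
- With a separate Exit Visit: 6 − 2 = 4 lost.
- With a 4-week visit that includes a CBC as well: 6 − 3 = 3 lost.

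Later breaks lose less: 3 − 1 = 2 at Day 37, 2 − 1 = 1 just after Day 50, and 1 − 1 = 0 after the Day 57 visit.

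**PK and receptor occupancy, break after the Day 15 visit.**

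- PK remaining: Days 22, 29, 30–32, 36 pre-dose, 36 post-dose, 37–39, 40–42, 43, 50, 64 = 10. Lost: 10 − 1 = 9.
- Receptor occupancy remaining: Days 29, 30–32, 36, 37–39, 40–42, 43, 50, 64 = 8. Lost: 8 − 1 = 7.

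Some of these samples are tied to doses that would not be given.

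**New AEs.** After Day 15, AEs are recorded at 11 further scheduled visits: Days 22, 29, 30–32, 36, 37–39, 40–42, 43, 50, 57, 64 and 71. After removal, the required withdrawal or exit set remains. Beyond it come the recommended 4-week visit, which falls on Day 15 + 28 = Day 43 for a last dose on Day 15, and contact as needed.

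**The case against.** Code breaks are rare by design and may be zero, and an emergency need not be drug-related. Any event that prompted the break must be followed under Section 9.5, with extra laboratory tests where indicated. The counts above therefore measure scheduled samples, not safety information lost outright. All of this stands, and it is why the point is low severity.

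Four stronger readings are tempting, and the documents do not support them.

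- **AE detection ends at removal.** Known AEs are followed, an exit assessment is required and contact continues. Section 9.3.1 is also ambiguous: its mention of the follow-up period can be read as covering patients who have left. The supportable statement is that enquiry about new AEs is no longer fixed by a schedule.
- **The patient leaves the analysis.** SAP 4.1 keeps every randomized patient with at least one dose in the Intent-to-Treat population, and every dosed patient in the Safety population. Only later data are affected.
- **The trial's validity is at risk.** No unblinding rate is given, so nothing supports a trial-level effect.
- **Only PK and receptor-occupancy samples from Day 43 on matter after a Day 15 break.** That would discard Days 22 and 29, about 7 and 14 days after the last dose. Section 3.2.1 places receptor occupancy after a single dose at up to Day 8 for 2.0 mg/kg and about Day 15 for 4.0 mg/kg, so these are the washout samples closest to the activity window.

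**Conclusion.** The point holds as a cheap improvement of low severity. Removal from the study goes further than stopping drug, and no reason is given for the difference. After one withdrawal or exit set, new-AE enquiry becomes as-needed and scheduled safety laboratory samples lapse. Up to two antibody samples are lost per patient, and the late Day 64 sample is lost for any break before it.

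The counts rest on Sections 10.2.7 and 10.3.2 governing the withdrawal visit, and on the break falling after that day's samples unless stated. The figure of 3 lost CBCs also assumes that the 4-week visit includes one, since Section 7.1 does not give its content.

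**What to change.** In Protocol 5.4 and SAP 3.4, replace removal with wording such as: *study drug is permanently stopped (the resumption provision of Section 3.5 does not apply), and the subject continues the scheduled AE, safety laboratory and antibody assessments through Day 71 unless consent is withdrawn.* With this, no scheduled antibody sample or blood count is given up. If PK or receptor-occupancy washout samples are also wanted, name them by day.

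In the SAP, flag AE causality judgements and any DAS28-CRP or ACR assessments made after unblinding. Protocol 9.6 does not allow the blind to be broken in order to judge causality. SAP 4 and 9.1 take the last treatment-period assessment as the end-of-treatment value, and that may be a visit held after the code break. Excluding such scores is optional, as a sensitivity analysis: a patient unblinded before any post-baseline score would then have no value.

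The cost is a protocol amendment with ethics approval (Section 13.3), re-consent if the consent form is revised (Section 13.4), and a few already scheduled visits for a rare patient. SAP 3.5 reports 41 subjects already randomized, so the protocol wording helps only patients still on study or a successor protocol. The SAP flag can be added at any time before database lock.
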